9.3 Missing Data

No missing data will be imputed

9.4 Statistical Methodology

9.4.1 Data Summary

Descriptive statistics will be computed for all baseline conditions and demographic parameters. That is, for continuous data, the N, mean, median, standard deviation, minimum and maximum will be computed. For categorical data, the frequency will be computed. The data will be presented by appropriate subgroups (e.g., center, gender).

A Kaplan-Meier survivorship curve will be displayed for revision and/or removal of the Triathlon total knee arthroplasty cemented with Simplex HV for aseptic loosening.

A Kaplan-Meier survivorship curve will be displayed for all-cause revision and/or removal of the Triathlon total knee arthroplasty cemented with Simplex HV with Gentamicin for aseptic loosening.

Two year Kaplan-Meier success rate with 95% CI will be presented.

For all additional data collected that are not required for direct support of a study objective, data will be summarized according to follow-up. For parameters represented by continuous variables (e.g., ROM), the summaries will consist of the N, mean, median, standard deviation, minimum, and maximum values.

Documentation of statistical analyses utilizing SAS® software version 9.3 or higher will be maintained.

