Objectives	
Primary:
 
To evaluate the success rate of cemented Triathlon Total Knee components implanted using Simplex high viscosity bone cement (Simplex HV). Success is defined as absence of revision due to aseptic loosening in cemented Triathlon Total Knee components implanted with Simplex HV at 24 months.
 
Secondary:
 
To review OKS, KSS results and complications of patients who have received Simplex HV in a Triathlon Total Knee Arthroplasty.

Number of Cases	A minimum of 100 Simplex HV cases and 100 Simplex HV-Gentamicin cases who have received cemented Triathlon Total Knee System will be enrolled.
Inclusion/Exclusion Criteria	
Inclusion Criteria:
 
 A. The Patient is age 18 or over at time of study device implantation B. Patients who have undergone primary Triathlon Total Knee Arthroplasty in which Simplex HV/Simplex HV Gentamicin was indicated for fixation and used on label C. Patients who have been followed for at least 24 months postoperatively 
Exclusion Criteria:
 
 A. Patients who have undergone revision surgery B. Patients who have undergone bilateral Knee Arthroplasty C. Patients contraindicated for either the devices implanted, or the cement used, according to medical history review and instructions for use D. Patient has a cementless tibial baseplate. E. Patient has an active or suspected latent infection in or about the affected knee joint F. Patient has muscle loss or neuromuscular impairment in the affected limb that would create an unjustifiable risk

	
G. Patient is immunologically suppressed or receiving steroids in excess of normal physiological requirements (e.g. > 30 days)
 
H. Patient has a known hypersensitivity to any of the cements constituents or in patients with severe renal failure
 
I. Patient is a prisoner

Study Device	
Bone Cement:
 
• Simplex® HV• Simplex® HV with Gentamicin
Statistical Methodology	
• No sample size calculation because a number of 100 cases per study arm was pre-defined by the regulatory body.• The success rate at two years will be presented with 95% confidence interval.• Frequency and percentage will be presented in tabular form for categorical variables. The mean, standard deviation, minimum and maximum values will be presented for quantitative variables.

Evaluation Schedule

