9.1 Study Objectives

9.1.1 Objective Analysis

To evaluate the success rate of cemented Triathlon Total Knee components implanted using Simplex high viscosity bone cement (Simplex HV). Success is defined as absence of revision of cemented Triathlon Total Knee components implanted with Simplex HV for aseptic loosening at two years postoperative. 95% confidence interval of the success rate will be presented as well.

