9.4.4 Analysis Population

Per Protocol Population: The study population will include all non-censored subjects who have received the Triathlon total knee system cemented with Simplex HV and are available for objective analysis.

The objective analyses will be based on the per protocol population.

Safety Population: The safety population will include all non-censored subjects who received the Triathlon total knee system cemented with Simplex HV.

The safety analysis will be based on the safety population.

10 Study Monitoring, Auditing, and Inspecting

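### Section 9.4.1 specifies the Kaplan-Meier event for Simplex HV with Gentamicin as both all-cause and for aseptic loosening; the event should match the other curve and the endpoint in 9.1.1

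*Combined protocol and SAP*

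**What the plan says.** Section 9.4.1 plans two survivorship curves in consecutive sentences. The first is for "revision and/or removal of the Triathlon total knee arthroplasty cemented with Simplex HV for aseptic loosening". The second, for the gentamicin cement, is for "all-cause revision and/or removal of the Triathlon total knee arthroplasty cemented with Simplex HV with Gentamicin for aseptic loosening". The next sentence promises the estimate: "Two year Kaplan-Meier success rate with 95% CI will be presented".

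The primary endpoint is defined twice, both times by cause. Section 9.1.1 reads: "Success is defined as absence of revision of cemented Triathlon Total Knee components implanted with Simplex HV for aseptic loosening at two years postoperative". The synopsis reads: "Success is defined as absence of revision due to aseptic loosening in cemented Triathlon Total Knee components". Section 3.1 describes Simplex HV as available with and without gentamicin, so this definition covers both cements. The synopsis asks for "A minimum of 100 Simplex HV cases and 100 Simplex HV-Gentamicin cases", so the gentamicin curve describes about half of the study.

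**The concern.** The gentamicin sentence contains two event definitions that exclude each other. An all-cause curve counts every revision or removal. A curve for aseptic loosening counts only those done for that reason and has to treat the rest in some other way.

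A programmer who followed the first word would build a gentamicin curve on a different event from the Simplex HV curve beside it. That curve would not estimate the success rate in 9.1.1. Readers will naturally set the two curves side by side, even though no test is planned, and could take a difference in definition for a difference between cements. The gap need not be empty: section 1.1 names infection, ahead of loosening, as the most common reason for failure of a total knee arthroplasty.

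**Working it through.** The plan gives no figure to reproduce. Section 9.4.2 states that there is no sample size calculation, and no revision rate is assumed anywhere.

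**Step 1: the passages side by side.**

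| Place | Event or item | Cause |
|---|---|---|
| Synopsis, Objectives | revision | aseptic loosening |
| 9.1.1 | revision | aseptic loosening |
| 9.4.1, Simplex HV curve | revision and/or removal | aseptic loosening |
| 9.4.1, gentamicin curve | revision and/or removal | all causes *and* aseptic loosening |
| 9.2.1, safety parameters | revision and/or removal rates | no restriction |
| Appendix B, Follow-up form, item 6 | serious adverse event or device deficiency | aseptic loosening, or other reason |
| Appendix B, Adverse Event Report, Treatment | revision/removal, with a revision date | aseptic loosening |

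Only the gentamicin row contradicts itself. The endpoint definitions, the other curve and the two forms favour aseptic loosening. Only 9.2.1 mentions revision without a cause, and it does so as a safety parameter.

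**Step 2: how far the two readings can differ.** Inputs: n = 100 gentamicin knees (synopsis, the minimum) and full follow-up to 24 months (in line with inclusion criterion C in 5.1). Two assumptions are mine: revised knees stay in the cohort, and the event counts are illustrative.

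Let k be the number of other-cause revisions, with no revision for aseptic loosening. With no earlier loss, the all-cause Kaplan-Meier estimate is 1 − k/100. The aseptic-loosening estimate, with those k knees censored, has no events and stays at 100%. The plan does not name a method for the confidence interval; exact binomial lower limits for the all-cause rate are shown for scale.

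| k | All-cause estimate | Exact 95% lower limit | Aseptic-loosening estimate |
|---|---|---|---|
| 0 | 100% | 96.4% | 100% |
| 1 | 99% | 94.6% | 100% |
| 2 | 98% | 93.0% | 100% |
| 3 | 97% | 91.5% | 100% |

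Now add one revision for aseptic loosening. The all-cause estimate is 1 − (k + 1)/100, which gives 98%, 97% and 96% for k = 1, 2 and 3. The aseptic-loosening estimate depends on order:

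- If the loosening comes first: 1 − 1/100 = 99.00%.
- If it comes after all k censored knees: 1 − 1/(100 − k), that is 1 − 1/99 = 98.99%, 1 − 1/98 = 98.98% and 1 − 1/97 = 98.97%.

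So each other-cause revision costs 1 point on the all-cause reading and at most about 0.01 point on the other.

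**Step 3: the condition.** Exclusion criterion A in 5.1 excludes patients who have undergone revision surgery. Taken literally to include revision of the study knee, it leaves no revised knees, and both readings give 100%. That is a separate problem; the sizes in step 2 assume it does not apply.

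**The case against.** The strongest reply is that this is one stray term in a descriptive curve. The primary event is defined in the synopsis and in 9.1.1, no test between cements is planned, and the forms support the aseptic-loosening reading: the only dedicated revision item, with its date, is for that cause. All of this stands, and it limits the consequence. It does not remove the contradiction, because 9.4.1 is the section from which the curve would be programmed.

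A second reply is that the word may be the remnant of an intended all-cause analysis. Section 9.2.1 lists revision and/or removal rates without a cause, yet 9.2.2 tabulates only adverse events. Simply deleting the word would remove the only all-cause survivorship analysis in the plan. This stands too, and the fix allows for it.

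Three stronger readings are tempting, and the documents do not support them:

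- A reader might infer that the primary endpoint is undefined. It is not: both definitions name aseptic loosening. Nor does the two-year rate lack a natural source, since it follows directly after two curves given by cement.
- A reader might infer that a comparison of the cements is invalidated. None is planned.
- A reader might link the censoring of other-cause revisions to 9.4.4, where "The study population will include all non-censored subjects who have received the Triathlon total knee system cemented with Simplex HV", and conclude that such knees would be dropped. In a Kaplan-Meier analysis every event-free knee is also censored at the end of its follow-up, so that reading would drop all event-free knees and not just these. The term is undefined, but that is a separate matter.

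The added words on removal in both curves and the unnamed interval method are also separate gaps in detail.

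**Conclusion.** The gentamicin sentence in 9.4.1 is wrong as written and should be corrected. The rest of the document favours aseptic loosening. If all-cause were followed instead, one of the two cements would be shown on a different event from the other and from the primary endpoint.

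The size is 1 percentage point per other-cause revision among 100 knees, against essentially no change on the aseptic-loosening reading. This rests on full 24-month follow-up, on keeping revised knees in the cohort and on assumed event counts; it is zero if exclusion A removes revised knees. The likely harm is a mismatched or mislabelled curve, not a wrong test or an undefined primary result. It is worth fixing before analysis: the outcomes in a retrospective study already exist, so an event chosen after seeing them would be open to challenge.

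**What to change.** In 9.4.1:

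- Delete all-cause from the gentamicin sentence, so that both curves use revision for aseptic loosening as in 9.1.1, labelled Simplex HV non-medicated and Simplex HV with Gentamicin.
- State that a knee revised for another cause is censored at that revision.
- State that the two-year success rate with 95% CI is taken from these curves for each cement.
- Because 9.2.1 lists revision and/or removal rates without a cause restriction, add all-cause revision/removal as a separately labelled curve for both cements.

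The cost is a few sentences and a small amount of extra analysis, with no new patients or visits. There is one practical burden. The Adverse Event Report shows a revision date only on the aseptic-loosening line, and other operations on the knee fall under a free-text option. The date of an other-cause revision may therefore have to come from the adverse event dates, the free text or the source files.

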1.1 Background

The American Joint Replacement Registry (AJRR) shows an annual increase from approximately 20,000 to almost 130,000 in primary TKAs from 2012 to 2017. In the same time the use of High Viscosity Cement (HVC) in primary knee arthroplasty increased steadily from 46% to 61%¹.

Most of commercially available acrylic bone cements are based upon polymethylmethacrylate (PMMA) and methylmethacrylate (MMA) systems and consist of powdered and liquid components². The polymerization of bone cement occurs through a progression of 4 phases: mixing phase, waiting phase, working phase, and hardening phase. HVC has some advantages over low-viscosity cement (LVC) including shorter mixing and waiting phases, whereas the working and hardening phases are longer. Operational efficiencies are receiving greater interest by surgeons and hospital administrations because high viscosity (HV) bone cements provide a shorter dough time than medium viscosity cements, which may result in surgical efficiencies by

allowing surgeons to handle and apply the cement to implant components and bone earlier while having more time to work with the cement during implantation of the components.^{1,2,3}.

The most common reason for failure of TKA is infection followed by implant loosening, polyethylene wear, and instability⁴. With the use of HVC, the literature describes a focus on aseptic loosening of the tibial component probably resulting from debonding of the cement-tray interface^{3,4}. Considering the exact cause may be unknown, some authors suggest associations of this type of failure to the use of high-viscosity cement^{5,6}. In contrast, a retrospective review of 1851 cases of primary TKA (obese patients with BMI >35) using HVC mixed with Gentamicin showed one revision due to aseptic loosening³.

This study is a retrospective investigation of subjects who have received primary Triathlon Total Knee Arthroplasty inserted with Simplex High Viscosity (HV) Cement to evaluate the success rate defined as absence of revision for aseptic loosening of components at two years postoperative.

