5.1 Inclusion/Exclusion Criteria

Inclusion Criteria:

- A. The Patient is age 18 or over at time of study device implantation
- B. Patients who have undergone primary Triathlon Total Knee Arthroplasty in which Simplex HV/Simplex HV Gentamicin was indicated for fixation and used on label
- C. Patients who have been followed for at least 24 months postoperatively

Exclusion Criteria:

- A. Patients who have undergone revision surgery
- B. Patients who have undergone bilateral Knee Arthroplasty
- C. Patients contraindicated for either the devices implanted, or the cement used, according to medical history review and instructions for use
- D. Patient has a cementless tibial baseplate.
- E. Patient has an active or suspected latent infection in or about the affected knee joint
- F. Patient has muscle loss or neuromuscular impairment in the affected limb that would create an unjustifiable risk
- G. Patient is immunologically suppressed or receiving steroids in excess of normal physiological requirements (e.g. > 30 days)
- H. Patient has a known hypersensitivity to any of the cements constituents or in patients with severe renal failure
- I. Patient is a prisoner

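### No method is named for the 95% interval on the two-year success rate; with no failures, the usual Kaplan-Meier formulas give 100% to 100% or no interval

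*Combined protocol and SAP*

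**What the plan says.** The interval is promised in three places:

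- Synopsis, Statistical Methodology: "The success rate at two years will be presented with 95% confidence interval".
- Section 9.1.1: "95% confidence interval of the success rate will be presented as well".
- Section 9.4.1: "Two year Kaplan-Meier success rate with 95% CI will be presented".

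Only Section 9.4.1 ties it to Kaplan-Meier. No variance estimator, transformation or zero-event rule appears there, nor in Sections 9.3, 9.4.2, 9.4.3 or 9.4.4. The software is SAS 9.3 or higher, with no procedure or option named. Section 9.4.2 takes 100 cases per arm as set by the regulatory body.

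Other text decides what the interval would describe:

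- Inclusion C (Section 5.1) admits "Patients who have been followed for at least 24 months postoperatively", and Section 9.4.4 limits the analysis to subjects who are not censored.
- Table 1 and Section 5.4 place the visit at 24 (+2) months. The follow-up, KSS and OKS forms in Appendix B offer a box for 12 to 24 (+2) months.
- Exclusion A removes "Patients who have undergone revision surgery", without saying whether this means before or after the study operation.
- In Section 9.4.1 the gentamicin curve is for "all-cause revision and/or removal of the Triathlon total knee arthroplasty cemented with Simplex HV with Gentamicin for aseptic loosening", which names two different endpoints at once.

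**The concern.** This interval is the only planned statement of uncertainty on the primary endpoint. Revision for aseptic loosening within two years may well be rare enough that a group of 100 knees has none. The standard Kaplan-Meier intervals break down in exactly that case. The report would then show either complete certainty drawn from 100 knees or a blank, although the data would be compatible with a true failure rate of up to 3.6%.

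With a single failure the methods also disagree by several points at the lower limit. Because none is named, the choice could be made after the result is known.

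**Working it through.** **Nothing to reproduce.** The sample size is not derived from a rate, margin or interval width, so there is no stated figure to recover.

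**Inputs.** n = 100 per cement group (Section 9.4.2). The only event rate in the documents is in Section 1.1: a "retrospective review of 1851 cases of primary TKA (obese patients with BMI >35) using HVC mixed with Gentamicin showed one revision" for aseptic loosening, that is 1/1851 = 0.054%. All other rates below are assumptions.

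**Probability of no failures in 100 knees,** (1 − p)^100:

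| True failure rate p | P(0 of 100) |
|---|---|
| 1/1851 | 94.7% |
| 0.5% | 60.6% |
| 1% | 36.6% |
| 2% | 13.3% |
| 3% | 4.8% |

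**No failures, 100/100.** With no censoring, S = 1 and the Greenwood standard error S·√[d/(n(n − d))] is 0.

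- Linear, S ± 1.96·SE: 100% to 100%.
- Log: 100% to 100%.
- Log-log: requires ln(−ln 1) = ln 0 and divides by ln 1 = 0, so it is undefined.
- Exact (Clopper-Pearson): lower limit 0.025^(1/100) = 0.9638, so 96.4% to 100%. The upper bound on the failure rate is 1 − 0.9638 = 3.6%.

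**One failure, 99/100.** SE = √(0.99 × 0.01/100) = 0.00995.

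| Method | 95% interval |
|---|---|
| Linear | 97.0% to 101.0% |
| Log | 97.1% to 101.0% |
| Log-log | 93.1% to 99.9% |
| Exact | 94.6% to 99.97% |

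The lower limit varies by about 4 points (97.1 − 93.1), and two of the upper limits exceed 100%.

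**Per group or pooled.** With no failures the exact lower limit is 96.4% for one group of 100 and 0.025^(1/200) = 98.2% for both groups pooled.

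**Counting rule.** Suppose no knee is revised for aseptic loosening and one is revised for another cause before 24 months. The exact lower limit is 96.4% if that knee counts as a success (100/100), 96.3% if it is dropped (99/99), and 94.6% if it counts as a failure (99/100).

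**Early censoring.** If knees last seen before 24 months are entered, fewer have a known 24-month status. With no failures the exact lower limit becomes 96.0% at 90 knees and 95.5% at 80 (assumed numbers). Once there is a failure, the Kaplan-Meier estimate and the simple proportion can also differ.

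**Coverage of the exact interval at n = 100.** At p = 0.5% it contains the truth for 0 to 2 failures, probability 98.6%. At p = 1% it does so for 0 to 3 failures, probability 98.2%.

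**The case against.** The strongest reply is that little depends on this interval. The study is descriptive, with no hypothesis test or performance goal. Revision rates are safety parameters under Section 9.2.1, so a reader who sees 0 of 100 can work out 96.4% to 100%. A degenerate or blank interval would be noticed and would not mislead silently. This stands, and it limits the weight of the point.

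The plan is also silent; it does not prescribe a failing method. A reader might infer that it commits the sponsor to an interval that collapses. It does not: an exact binomial interval already satisfies the synopsis and Section 9.1.1, and the Greenwood formula is an assumption even for Section 9.4.1. What remains is that nothing excludes the usual formulas.

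Nor is zero failures known to be the expected result. The 94.7% rests on a series of obese patients given gentamicin-mixed cement, and Section 1.1 also reports that "some authors suggest associations of this type of failure to the use of high-viscosity cement". The range across the rates shown is 4.8% to 94.7%. If the gentamicin curve is meant to be all-cause, zero events is less likely for that curve.

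Finally, naming an interval method does not settle everything. Per group against pooled, and the handling of a knee revised for another cause, each move the lower limit by up to 1.8 points (98.2 − 96.4; 96.4 − 94.6). A fix that left them open would be incomplete.

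**Conclusion.** The point holds as a modest improvement to the reporting of the primary result. The method is missing in all three places. With no failures in a group of 100, Greenwood-based intervals would give 100% to 100% or nothing, where the exact interval is 96.4% to 100%. With one failure, the choice of method moves the lower limit between 93.1% and 97.1%.

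Two stronger readings are not supported. A reader might infer that only the interval is open, because Inclusion C makes Kaplan-Meier and the simple proportion coincide. They coincide if every knee's status is known at 24 months, but the window on the Appendix B forms would allow shorter follow-up, and the restriction to uncensored subjects in Section 9.4.4 leaves the denominator unclear. A reader might also infer that an exact interval makes the result sound. If Exclusion A removes knees whose study implant was revised, the absence of failures is produced by selection, and neither 96.4% to 100% nor any other interval is informative. That question must be resolved separately.

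**What to change.** Keep the Kaplan-Meier curves and estimate. Add to Sections 9.1.1 and 9.4.1: *For each cement group separately, the 95% CI for the 24-month success rate (absence of revision for aseptic loosening) is the exact Clopper-Pearson binomial interval, including when no failures occur.*

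Alongside it:

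- Fix the denominator before the data are reviewed: knees with a known status at 24 months. Count a knee revised for another cause before 24 months by one pre-stated rule, and show the result under the alternative count.
- Report how many knees have less than 24 months of follow-up.
- Reconcile the 12 to 24 (+2) month box on the Appendix B forms with the 24 (+2) month schedule and Inclusion C.
- State which endpoint the gentamicin curve uses.

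The cost is a sentence in two sections, a counting rule and a correction to the forms, with no new data. The downside is that the exact interval is slightly conservative, with coverage of about 98% to 99% at true failure rates of 1% and 0.5%.

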Evaluation	Pre-operative	Intra-operative	24 (+2) months post-operative	27 months up to 5 years post-operative
Inclusion/Exclusion	x			
Demographics & Medical History	x			
KSS	x		x	optional
Surgical Details		x		
Implant and Cement Details		x		
OKS	x		x	optional
A/P and Lateral X-ray Interface			x	optional
Adverse Events		x	x	per protocol

Table 1 Evaluation Schedule

1 Introduction

This document is a protocol for a retrospective human research study. This study will be conducted in compliance with the protocol, international standard ISO 14155 Standards, associated Federal regulations and all applicable research requirements.

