5.2 Pre-operative Data Collection

- Patient demographics
- Diagnosis/reason for the primary total knee arthroplasty, operative side
- Preoperative medical history: Relevant concurrent medical condition and treatment
- Knee Society Score (KSS)
- Oxford Knee Score

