5.4 Post-operative Data Collection

Data collection at 24 months (+ 2 months) postoperatively and optional at 5 years postoperative.

- Knee Society Score (KSS)
- Oxford Knee Score (OKS)
- X-ray collection for independent analysis
 - A/P view
 - Lateral view
- Elective surgery since study surgery
- Post-operative Adverse event or device deficiency

6 Adverse Events

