 Gastrointestinal tract/metabolism			 No treatment			 Treatment						
 Blood and blood forming organs			 No treatment			 Treatment						
 Cardiovascular system			 No treatment			 Treatment						
 Skin			 No treatment			 Treatment						
 Reproductive system			 No treatment			 Treatment						
 Endocrine system			 No treatment			 Treatment						
 Infections and Infestations			 No treatment			 Treatment						
 Malignant/Immune disease			 No treatment			 Treatment						
 Muscles, bones and joints			 No treatment			 Treatment						
 Brain and nervous system			 No treatment			 Treatment						
 Respiratory system			 No treatment			 Treatment						
 Other			 No treatment			 Treatment						
 Other			 No treatment			 Treatment						
Investigator Name (Print)						For Stryker Use Only			INITIAL/DATE:			
						Stamp Date Received:			Monitored:	/		
									Receipt:	/		
									Entry:	/		
									Verification:	/		
Investigator Signature												
Date												
									D D	M M M	Y Y Y Y	

Stryker® Simplex HV Retrospective Study			
Page 1 of 1	Knee Society Score	Patient ID 8 0	
		Study#	Center#
		Subject#	Side (L/R)
GENERAL INFORMATION			
Patient code (Use AA, BB,...AB)		Date of examination 	
Pre-op visit 	Follow-up at  12-24 months (+2 months) post study surgery  5 years (± 3 months) post study surgery, specify  years  months		

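### OKS and KSS are collected before surgery and at 24 months, but the plan specifies only descriptive summaries and no within-patient change

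*Combined protocol and SAP*

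**What the plan says.** The secondary objective in the synopsis is "To review OKS, KSS results and complications of patients who have received Simplex HV in a Triathlon Total Knee Arthroplasty". Table 1 and Section 5.2 schedule both scores pre-operatively. Table 1 schedules them again at "24 (+2) months post-operative", and Section 5.4 agrees: "Data collection at 24 months (+ 2 months) postoperatively and optional at 5 years postoperative".

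Section 9.1.1 gives an analysis for the primary success rate only. For other data, Section 9.4.1 opens with a scope limit, "For all additional data collected that are not required for direct support of a study objective", and continues "data will be summarized according to follow-up". Continuous variables get the count, mean, median, SD and range, with range of motion (an item on the KSS form) as the example. The synopsis prescribes mean, SD and range for quantitative variables in general. Section 9.3 states "No missing data will be imputed".

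Nowhere is there a change score, an interval for a change, or an analysis set of patients with both scores. The KSS and OKS forms in Appendix B label the first follow-up as "12-24 months (+2 months) post study surgery".

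**The concern.** The design produces before-and-after pairs on two functional scores, and the planned output does not use them. A reader who sees a pre-operative mean beside a 24-month mean is likely to subtract one from the other and read the result as improvement. Two things can then go wrong.

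First, each mean rests on whoever has a score at that visit. If some scores are absent, the difference need not be the improvement of any defined group of patients.

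Second, even if every patient has both scores, the spread at each visit does not determine the spread of the change. The tables would therefore show an apparent gain with no usable measure of its precision.

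**Working it through.** The documents give no SD, between-visit correlation or missing-data rate for OKS or KSS, so there is no planned figure to reproduce. The only input from the plan is n = 100 per cement type (synopsis; Section 9.4.2). The correlations, availability rates and score differences below are assumptions, used only for scale.

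**1. Which rule covers the scores?** Read literally, the Section 9.4.1 sentence excludes data that directly support an objective, and OKS and KSS are named in one. On that reading only the synopsis descriptives apply. If *objective* means the one analysed in Section 9.1.1, the visit-wise rule applies. Neither reading gives a within-patient change.

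**2. Can scores be missing?** Section 4.1 draws the data from routine-care records. The KSS form has boxes to record that the pain/motion or function part was not performed. The eligibility criteria require 24 months of follow-up but no score at either visit, and the populations in Section 9.4.4 do not require both scores. Missing scores are therefore plausible, but their frequency is unknown.

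**3. How far could the two visit groups differ?** If shares a and b of 100 patients have a pre-operative and a 24-month score, the number with both lies between 100 × max(0, a + b − 1) and 100 × min(a, b).

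- a = b = 0.8: 60 to 80 pairs
- a = 0.7, b = 0.8: 50 to 70 pairs
- a = b = 0.5: 0 to 50 pairs

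**4. How far could the difference of means move?** Suppose all patients have a 24-month score, a share f lacks the pre-operative one, and the true pre-operative mean of those patients differs by d SD from that of patients with a score. The difference of visit means then departs from the whole-cohort mean change by f × d. For f from 0.1 to 0.4 and d from 0.25 to 1.0 this runs from 0.1 × 0.25 = 0.025 SD to 0.4 × 1.0 = 0.40 SD. With f = 0 it is zero.

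**5. What is missing even with complete scores?** The variance of the change is s₁² + s₂² − 2ρs₁s₂. The tables would report s₁ and s₂ but not ρ. With equal SDs and n = 100, the 95% half-widths in SD units are:

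- visits treated as independent: 1.96 × √(2/100) = 0.277
- paired, ρ = 0.3: 1.96 × √(2 × 0.7/100) = 0.232
- paired, ρ = 0.6: 1.96 × √(2 × 0.4/100) = 0.175

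The ratio of paired to independent width is √(1 − ρ): 0.837 at ρ = 0.3 and 0.632 at ρ = 0.6. The paired interval is 16% and 37% narrower respectively.

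**The case against.** The best defence is that the objective is to review results. It states no improvement claim, hypothesis or comparison, so visit summaries are a legitimate descriptive answer. The counts are reported, so unequal denominators would be visible. Table 1 requires both scores before surgery and at 24 months. With complete data the difference of visit means equals the mean paired change. The plan computes no interval for these scores, so the precision comparison is not with anything the sponsor intends to publish.

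Most of this stands, and it keeps the point small. The interval comparison concerns what a reader could form from the tables, not a planned result. However, counts at each visit do not show how many patients have both scores, and a descriptive change needs no hypothesis.

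Three stronger readings are tempting and should be resisted:

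- A reader might infer that the paired information is lost. It is not: each form carries the patient ID and visit, so the pairing is absent only from the planned output.
- A reader might infer that the visit means will be biased. That depends on missingness, for which the documents give no rate.
- A reader might take the Section 9.4.1 sentence as plainly prescribing the OKS and KSS analysis. Its scope limit leaves that uncertain.

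**Conclusion.** The point holds as a low-priority improvement. Under either reading of Section 9.4.1, and under the synopsis rule, the plan provides no within-patient change for the scores named in its secondary objective. The certain consequence is that the planned tables cannot give a confidence interval for the mean change, even with complete scores. At assumed correlations of 0.3 to 0.6 and equal SDs, an interval that ignores the pairing would be replaced by one 16% to 37% narrower. The conditional consequence is that, if scores are missing, the visit means may describe different patients; its size cannot be estimated from the documents. The absence of imputation is not itself the fault. The gap is that no change score and no paired set are defined. The primary success rate is unaffected.

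**What to change.** Add to Section 9.4.1:

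> For OKS and KSS, the change from pre-operative to 24 months is summarised by cement type in patients with both scores (number of pairs, mean, SD, 95% CI), alongside the visit summaries, and baseline characteristics are shown for patients with and without both scores.

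The baseline display shows selection but does not remove it: patients lacking a score remain outside the paired result and may have changed differently.

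Also reconcile the follow-up window on the KSS and OKS forms ("12-24 months (+2 months) post study surgery") with the 24 (+2) month visit in Table 1 and Section 5.4, so that the change refers to one time point. As the forms stand, a 12-month score could enter a 24-month change.

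The cost is one sentence, one table and a correction to the form labels. No new data and no change in sample size are needed.
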